# 2.6.1 Adverse events (AEs)

Adverse Events (AEs) will be coded using MedDRA and will be reported by system organ class (SOC) and preferred terms (PT). AEs will be considered treatment emergent if occurring on or after the date of randomization. All AE tables will be reported for treatment emergent events. Non treatment emergent, during run-in, will be listed separately.

A summary table will be presented with number (No.) of subjects with Treatment Emergent Adverse Events (TEAEs), No. of subjects with serious TEAEs, No. of subjects with severe TEAEs, No. of subjects with related TEAEs, No. of subjects with at least one TEAE leading to discontinuation, and also the No. of TEAEs, severe TEAEs, serious TEAEs.

The total No. of subjects with at least one TEAE and the No. of TEAEs will be summarized in a table by SOC. PT. A similar table will be created for serious adverse events (SAEs). All

| Novartis | Confidential | Page 19 of 30          |
|----------|--------------|------------------------|
| SAP      |              | Study No. CLCZ696BFI03 |

TEAEs will also be tabulated by severity (mild, moderate and severe) and causality to the treatment (related, not related).

In listings of AEs the relative day counted from first administration of IMP (Day 1) will be presented together with the relative day from the latest administration of IMP (the actual dates will also be included).

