During the screening/run-in period, the subjects will receive valsartan treatment that will replace their previous ACEI or ARB HF therapy. Valsartan during the screening/run-in period may be dispensed by any member of the study team. The screening/run-in dose of valsartan (80 mg BID or 160 mg BID) will be decided by the investigator based on the subject's clinical status, prior HF therapy and concomitant medications. The subjects will have a scheduled safety and efficacy assessment visit during the screening/run-in period (screening visit 2 in the study schedule, Table 3). If deemed sufficient by the investigator, screening visit 2 can be performed remotely. If so, safety blood sampling, eligibility criteria review, adverse events and concomitant medication must be assessed.

Dose reduction of a loop diuretic is allowed during the screening/run-in to prevent hypotension. Unscheduled visits may be performed at any time during the screening/run-in period. Study visit should be performed as close proximity to the stated day in the study schedule (Table 3) as possible.

The subject has to tolerate at the minimum 80 mg BID valsartan at a stable dose for minimum of 4 weeks in order to be eligible for the treatment period. Before the PET-scan, a urine pregnancy test should be performed for female subjects of childbearing potential. During the baseline visit, PET-scan and echocardiography will be done and blood samples for biomarker assessment will be drawn. After all other study procedures are performed at the baseline visit and the subject is deemed eligible for the study, he/she will be randomized and start the double-blinded treatment period.

The results for the laboratory tests taken during the on-site screening visits do not need to be available before decision-making (i.e. starting valsartan treatment), but they have to be reviewed as soon as possible after they become available in order to ensure subject safety. All screening/run-in period laboratory results must be available and reviewed before randomization, except the results of the laboratory tests taken on the baseline visit, as randomization is performed on the same day as the baseline visit.

Adverse events and changes in concomitant medications will be recorded throughout the screening/run-in period.

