- no action taken (e.g. further observation only)
- [investigational] treatment dosage increased/reduced
- [investigational] treatment interrupted/withdrawn
- concomitant medication or non-drug therapy given
- non-drug therapy given
- patient hospitalized/patient's hospitalization prolonged (see Section 8.3.3.1.1 for definition of SAE)
- its outcome (not recovered/not resolved; recovered/resolved; recovering/resolving, recovered/resolved with sequelae; fatal; or unknown)

Once an adverse event is detected, it must be followed until its resolution or until it is judged to be permanent, and assessment must be made at each visit (or more frequently, if necessary) of any changes in severity, the suspected relationship to the study drug, the interventions required to treat it, and the outcome.

Information about common side effects already known about the investigational drug can be found in the Investigator Brochure (IB). This information will be included in the patient informed consent and should be discussed with the patient during the study as needed. Any new information regarding the safety profile of the medicinal product that is identified between IB updates will be communicated as appropriate, for example, via an Investigator Notification or an Aggregate Safety Finding. New information might require an update to the informed consent and has then to be discussed with the patient.

The investigator must also instruct each patient to report any new adverse event (beyond the protocol observation period) that the patient, or the patient's personal physician, believes might reasonably be related to study treatment. This information

must be recorded in the investigator's source documents; however, if the AE meets the criteria of an SAE, it must be reported to Novartis.

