### 9.2.7 Analysis of safety variables

### 9.2.7.1 Evaluation of adverse events

AEs reported during the study will be classified by system organ class (SOC) and preferred terms (PT) using the MedDRA coding system. AEs will be displayed in a frequency table by dose level and treatment arm. The number and proportion (%) of subjects having each AE will be tabulated by SOC and PT and dose level. Severity of the AEs (mild, moderate, severe) and causality to the study treatment will be

tabulated with subject and event counts. SAEs and other significant AEs will be evaluated case by case.

AEs occurring before and after the initiation of the double-blind treatment period will be reported separately.

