## 2.1.1 General definitions

| Baseline     | Generally, a baseline measurement refers to the last non-missing
assessment made before the first administration of randomized
treatment (baseline visit). This is valid for, for example, vital signs
and laboratory data, where a difference from baseline is derived.  |
|--------------|--|
| Relative day | The relative day of an event with a start date is derived as:
Relative day = (Start date) - (Baseline date) + 1
For events occurring or starting before baseline the relative day is
derived as:
Relative day = (Start date) - (Baseline date)
In this way, there will be no Day 0. Day 1 is the same day as
baseline, and Day -1 is the day before. |
| Date format  | All dates in analysis datasets and tables, listings and figures will be
in the format YYYY-MM-DD  |

| Treatment
Emergent | All Adverse Events occurring on, or after the day of randomization will be considered Treatment Emergent (TE)   |
|-----------------------|---|
| First drug date       | The first administration of randomized treatment is assumed to be
on the same day as randomization   |
| Last drug date        | The last day of randomized treatment (treatment end date) is stated
on the study termination page in CRF.  |
| By dose level         | In all cases where summaries are stated to be by dose level, then
data will be summarized by the final titrated dose level during the
run-in period, ie the stratification by dose. |

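### The treatment-emergent rule has no worsening clause, so a run-in AE that worsens, becomes serious or leads to discontinuation after randomisation is left out of the between-arm AE tables

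*SAP*

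**What the plan says.** SAP 2.6.1 sets the classification: "AEs will be considered treatment emergent if occurring on or after the date of randomization". The general definitions in SAP 2.1.1 repeat it in nearly the same words. The date of the event relative to randomisation is the only test.

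SAP 2.6.1 then fixes what is tabulated: "All AE tables will be reported for treatment emergent events. Non treatment emergent, during run-in, will be listed separately". The overview table described there counts subjects with any, serious, severe, related and discontinuation-causing TEAEs. The AE tables in SAP 5.6 (14.3.1) are all TEAE tables.

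The protocol collects AEs before randomisation as well. Section 7.1 says: "Adverse events and changes in concomitant medications will be recorded throughout the screening/run-in period". On follow-up of a detected event, Protocol 8.3.4 says that "assessment must be made at each visit (or more frequently, if necessary) of any changes in severity". On analysis, Protocol 9.2.7.1 says only: "AEs occurring before and after the initiation of the double-blind treatment period will be reported separately". It gives no rule for an event that spans the two periods.

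**The concern.** Every subject takes active valsartan before randomisation. Afterwards one arm changes drug, and the dose can be changed in either arm. An AE that began on valsartan and deteriorates under randomised treatment is therefore part of the safety comparison.

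Protocol 2.6 names hypotension, hyperkalaemia and renal impairment as the most commonly reported reactions to sacubitril/valsartan. It also lists renal impairment and renal failure as common with valsartan. Such an event could plausibly begin in the run-in and worsen later. If it is classed by its start date, the later deterioration does not enter the severe, serious or discontinuation counts by arm. In arms of 30, those counts will be small, so a single missing subject is visible.

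**Working it through.** No figure in the plan bears on this point, so the check is a comparison of text, followed by a scale calculation.

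**1. Is worsening covered anywhere in the rule?** SAP 2.1.1 and 2.6.1: no. SAP 5.1.2, on incomplete AE dates, compares one date with the first randomised dose and uses no date of worsening. The SAE definition in Protocol 8.3.4.1.1 does mention worsening of something pre-existing, but it defines seriousness and the SAP does not use it for classification.

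**2. Does occurring mean starting?** The SAP does not say so outright. It is the natural reading: SAP 2.6.1 sets the term against events during the run-in, and SAP 2.1.1 derives relative day from the start date.

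**3. How is later worsening recorded?** Protocol 8.3.4 reassesses severity within the event already recorded. Protocol 8.3.4.1.2 sends progression of an SAE in as follow-up to the original report, whenever it happens. Neither document tells sites to open a new AE record when an event worsens.

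**4. One event followed through (hypothetical).** An AE starts in the run-in, is mild and ongoing at randomisation, becomes severe in week 3 and leads to withdrawal.

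- Classification: start date before randomisation, so not treatment-emergent.
- Missing from: the overview counts of any, severe and discontinuation-causing TEAEs, and the SOC/PT tables overall, by severity and by relation.
- Still visible in: the AE listings (SAP 5.6, 16.2.7), the display of AEs leading to withdrawal (14.3.2), and the discontinuation reasons tabulated by treatment (SAP 2.3.1). Had it become serious, it would also be in the SAE listings.

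**5. Scale.** Inputs: 30 planned and 27 targeted completers per arm (Protocol 5.2). One omitted subject shifts an arm's proportion by 100/30 = 3.3 percentage points, or 100/27 = 3.7.

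The documents give no rate of run-in AEs that later worsen. For an assumed proportion p of randomised subjects with such an event, the expected number per arm is 30p, and the chance of at least one among 60 is 1 − (1 − p)^60:

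| Assumed p | Expected per arm | Chance of at least one in 60 |
|---|---|---|
| 1% | 0.3 | 45% |
| 3% | 0.9 | 84% |
| 5% | 1.5 | 95% |
| 10% | 3.0 | >99% |

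These values of p are assumptions. They show only that even a low rate makes at least one omission likely in a trial of this size.

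**The case against.** Several counter-arguments have force.

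**The event is not lost from the report.** A reader might infer that it survives only in the run-in listing. The listings and the disposition table named above show otherwise, and Protocol 9.2.7.1 has SAEs and other significant AEs evaluated case by case. This stands: the loss is confined to the AE tables.

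**The key reactions are measured directly.** Potassium and creatinine are summarised by visit and arm with shift tables (SAP 2.6.3), and blood pressure by arm with a shift table (SAP 2.6.4.1 and 5.6). This compensates in part. It does not restore counts by severity, seriousness or causality, and it does not cover other kinds of event.

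**Few events can be open at randomisation.** Exclusion criteria 6 to 9 remove subjects with persistent symptomatic hypotension, low eGFR, high potassium or high creatinine. Inclusion criteria require systolic pressure of 110-160 mmHg at randomisation and tolerated valsartan. This limits the number but does not make it zero: those exclusions apply only if the problem persists after concomitant medication is modified, and milder events of any kind are not barred.

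**Sites may in practice open a new record.** The CRF and its completion guidelines are not among the documents, and Protocol 8.3.4.1.2 does ask for a new report when an SAE occurs at a different time interval. This is a real uncertainty, but the written instructions on severity changes and SAE progression point to the original event.

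**Conclusion.** The gap is real and specific: a stated rule omits worsening, and it governs every AE table. The number of subjects affected is probably small and cannot be computed from the documents. The size that can be stated is 3.3 percentage points of an arm's proportion per omitted subject. The conclusion assumes that occurring means starting and that worsening is kept on the original AE record. It concerns descriptive safety reporting and does not touch the primary endpoint.

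Two stronger readings are tempting but unsupported.

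- **Size.** A reader might apply the 17.6% hypotension rate in Protocol 2.6 to 30 subjects (0.176 × 30 = 5.3), suppose that one or two of about five had it already in the run-in, and infer that 20-40% of cases are missed (1/5 to 2/5). That rate comes from a trial of over 8400 patients in a different setting, and the one or two is invented. A run-in episode that resolved, followed by a new non-serious one after randomisation, would count as treatment-emergent anyway.
- **Direction.** A reader might infer that the omission favours sacubitril/valsartan because only that arm changes drug. But valsartan subjects who start on 80 mg BID are to be up-titrated at visit 1 if clinically possible (Protocol 4.3), so run-in events can worsen in both arms. Moreover, by the equivalences in Protocol 2.3, a subject moved from valsartan 160 mg to sacubitril/valsartan 100 mg at first receives a lower valsartan-equivalent dose. The documents do not settle the direction.

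**What to change.** In SAP 2.1.1 and 2.6.1, define a TEAE as an AE that starts on or after the date of randomisation, or that started earlier and on or after that date worsens in severity, becomes serious or leads to discontinuation of randomised treatment. Using the word starts also removes the ambiguity in occurring. The cut-off should stay at the randomisation date, because SAP 5.1.1 notes that actual dosing dates and times are not captured.

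Before unblinding, query the run-in AEs still ongoing at randomisation for the date of any such change. The SAP was finalised shortly before database lock, so a query on these records is more workable than a new instruction to sites.

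The cost is two sentences in the SAP, a limited data query and slightly higher TEAE counts.

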
### 4.2 Randomization and blinding

The subjects will be randomized in a 1:1 ratio to one of the two treatment arms, either the sacubitril/valsartan treatment arm or the valsartan treatment arm. Stratified randomization will be used to achieve similar groups in terms of patients with renal insufficiency (GFR 45-60 or >60 mL/min/1.73m^2) and/or diabetes mellitus (on insulin or oral glucose-lowering therapy, no more than 50 % of patients in the study are allowed to be diabetic). The baseline HF therapy (the number of subjects that are on valsartan 160 mg BID at the time of randomization) will also be taken into account during randomization.

Study drug packages will be provided from Novartis with removable labels stating the treatment. Treatment allocation will be done by an un-blinded member of the study team who will remove the labels stating the treatment before distributing the study drug packages to the subjects.

The randomization will be generated by an independent statistician at using SAS®.

Sealed envelopes containing the individual treatment codes (randomization number and the corresponding treatment) will be stored adjacent to the investigational medicinal products (IMPs) until the end of the trial. In case of an emergency requiring immediate knowledge of the treatment administered, the code of an individual subject may be opened. The reasons for opening the code have to be documented and the subject has to be discontinued from the study. The study monitor and the sponsor should be immediately informed about breaking of the treatment code.

This study will be conducted in a double-blinded fashion regarding the treatment (i.e. sacubitril/valsartan or valsartan). As the sacubitril/valsartan and valsartan tablets differ in appearance, the study has to be performed in a double-dummy manner with the subjects taking one active tablet and one placebo tablet BID. The different

strengths of the two study drugs are not identical in appearance so the possible dose modification(s) during the treatment period cannot be performed in a blinded manner. However, the up-titration step will be aligned in both treatment arms – the subjects will start on valsartan (80 mg BID or 160 mg BID) or sacubitril/valsartan (100 mg BID) and there will be only one scheduled up-titration visit after the randomization. The subjects that start from valsartan 160 mg BID will have similar scheduled visit but will stay on the same dose.

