### Table 3. General study outline

Study event	Screening visit 1	Screening visit 2 (R)	Baseline	Visit 1	Visit 2  (R)	Visit 3
	-5 weeks	- 4 weeks	day 1	day 14	day 21	week 8 
Informed consent	X					
Medical and surgical history	X					
Demographics	Х					
Physical examination 	X	X*	Х	Х	X*	X
Blood pressure and heart rate 	X	X*	Х	Х	X*	X
Safety blood samples 	X	X	X	X	X	X
Blood biomarker samples			Х			X
Decision on up- or down-titration				Х	X*	
Eligibility criteria review	X	X	Х			
Urine pregnancy test 			Х			X
 C-acetate PET-scan			X			х
Echocardio- graphy			Х			х
Randomization			Х			
Valsartan dispensing 	X	X*				
Study drug dispensing 			Х	Х	X*	
Instruction on drug intake 	Х	X*	X	X	X*	
Return of drug supplies 	2	X*	X	X	X*	х
Compliance check 		X*	X	Х	X*	Х
Adverse events			X			
Concomitant medications			Х	22 - 7		

R – If deemed sufficient by the investigator, screening visit 2 and visit 2 can be performed remotely (i.e. by telephone). If so, safety blood sampling, (eligibility criteria for screening visit 2 only), adverse events and concomitant medication must be assessed. If the visit is performed as a remote visit, assessments marked with "\*" do not need to be performed.

Visit 2 is a safety visit to be performed only for subjects whose dose was modified on visit 1 and/or if clinically indicated based on the investigator's decision. For subjects whose dose is not up-titrated on visit 1, visit 2 may be omitted.

 Visit 3 will be performed after the study treatment has been on a stable dose for a minimum of 6 weeks. It may be performed before or after 8 weeks, based on when the last dose modification was performed.

 Physical examination is part of clinical assessment and will take place on every site visit.

 Blood pressure and heart rate will be measured in a seated position, after at least 5 min of rest.

 Safety blood samples may be collected 1-2 business day(s) before the scheduled visit (with the exception of screening visit 1).

 For female subjects of childbearing potential.

 Study drugs will be dispensed by an unblinded member of the study team during the double-blinded treatment period. Valsartan may be dispensed by any member of the study team during the screening/run-in period.

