The day the subject starts taking the double-blind study medication is Day 1 (i.e. day of randomization) and the subsequent visits will take place on Day 14 (visit 1) and Day 21 (visit 2). Study visits should be performed as close proximity to the stated day in the study schedule (Table 3) as possible. Ideally, the last dose modification is done on visit 1. Visit 2 is a safety visit to be performed only for subjects for whom the treatment dose was modified on visit 1 and/or if it is clinically indicated based on the investigator's decision. If deemed sufficient by the investigator, visit 2 can be performed remotely. If so, safety blood sampling, adverse events and concomitant medication must be assessed. For subjects whose dose is not up-titrated on visit 1, visit 2 may be omitted, based on investigator's decision that has to be documented. Unscheduled visits may be performed at any time during the treatment period. Dose modifications, including up- and possible down-titrations are permitted during the first 4 weeks of the treatment period. Every effort should be made that the highest tolerated dose is reached on visit 1, at the latest, and only down-titrations are done after that, if clinically indicated. If dose is modified (down- and/or up-titrated) within the first 4 weeks, an unscheduled visit should be performed to assess subject safety on the new dose level. As dose modifications may be performed at any visit, the subjects will be asked to return their study medication at each site visit. They will be given new study drug packages or the same study drug packages will be returned to them, as applicable, according to the investigator's decision on dose modification.

The subjects will have to be on a stable dose of study treatment for a minimum of 6 weeks before visit 3. Visit 3 will include safety assessments (BP and safety laboratory tests), blood samples will be obtained for biomarker analysis and PET-scan and echocardiography will be performed. Before the PET-scan, a urine pregnancy test should be performed for female subjects of childbearing potential. The study ends for a subject after the last assessment is performed during visit 3; there will be no separate end-of-study visit. The subject will return the study medication to the site and he/she will continue his/her normal HF therapy, as advised by the investigator.

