# 8.3.4 Adverse events

An adverse event (AE) is any untoward medical occurrence (e.g., any unfavorable and unintended sign (including abnormal laboratory findings), symptom or disease) in a subject or clinical investigation subject after providing written informed consent for participation in the study until the end of study. Therefore, an AE may or may not be temporally or causally associated with the use of a medicinal (investigational) product.

In addition, all reports of intentional misuse and abuse of the product are also considered an adverse event irrespective if a clinical event has occurred.

The occurrence of adverse events must be sought by non-directive questioning of the patient at each visit during the study. Adverse events also may be detected when they are volunteered by the patient during or between visits or through physical examination findings, laboratory test findings, or other assessments.

Abnormal laboratory values or test results constitute adverse events only if they fulfill at least one of the following criteria:

- they induce clinical signs or symptoms,
- they are considered clinically significant,
- they require therapy.

Clinically significant abnormal laboratory values or test results must be identified through a review of values outside of normal ranges/clinically notable ranges, significant changes from baseline or the previous visit, or values which are considered to be non-typical in patient with underlying disease. Investigators have the responsibility for managing the safety of individual patient and identifying adverse events.

Adverse events must be recorded in the appropriate CRF capturing AEs under the signs, symptoms or diagnosis associated with them, accompanied by the following information:

- the severity grade
  - mild: usually transient in nature and generally not interfering with normal activities
  - moderate: sufficiently discomforting to interfere with normal activities
  - severe: prevents normal activities
- its relationship to the study treatment
- its duration (start and end dates) or if the event is ongoing an outcome of not recovered/not resolved must be reported.
- whether it constitutes a serious adverse event (SAE See Section 8.3.3.1.1 for definition of SAE) and which seriousness criteria have been met.
- action taken regarding [investigational] treatment

All adverse events must be treated appropriately. Treatment may include one or more of the following:

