# 2 Statistical methods

# 2.1 Data analysis general information

The statistical analyses in this study will be conducted by the CRO using SAS 9.4M3. At the raw data generated by electronic data capture (EDC) system will be combined to applicable analysis data sets, as required, and statistical output will be generated based on these aggregated data sets.

All data will be tabulated using summary statistics and/or listed. For continuous data both absolute values and the corresponding changes form baseline will be presented, and the following summary statistics will be included; number of observations, mean, standard deviation, minimum, first quartile, median, third quartile and maximum. In addition gemetric mean and coefficient of variation may be provided in the summaries of efficacy endpoints, as applicable.

Categorical data will be presented as counts and percentages, i.e., n (xx.x%). Changes form baseline in categorical data will be displayed in shift tables. Percentages will be based on the number of subjects in the analysis data set used.

Summary statistics will be presented by randomized treatment group and in total, and by visit and assessment time, as applicable. In addition, summary statistics may be presented by final titrated dose group during run-in period and other stratification factor levels as described in the each section of this document.

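### Adverse events are shown as crude counts by arm although follow-up can differ in length between arms; adding time at risk is a cheap improvement

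*SAP*

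**What the plan says.** **Analysis.** For TEAEs, SAP 2.6.1 states: "The total No. of subjects with at least one TEAE and the No. of TEAEs will be summarized in a table by SOC". Serious events get a similar table. The general rules in SAP 2.1 add "Summary statistics will be presented by randomized treatment group and in total" and "Percentages will be based on the number of subjects in the analysis data set used", so the denominator is subjects, not time. The TEAE window has a start but no stated end: "AEs will be considered treatment emergent if occurring on or after the date of randomization".

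**End of collection.** Protocol 8.3.4 counts events "after providing written informed consent for participation in the study until the end of study", and Protocol 7.2 fixes that end: "The study ends for a subject after the last assessment is performed during visit 3". Serious events are reported for a further 30 days (Protocol 8.3.4.1.2).

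**Timing of visit 3.** Footnote 2 to Table 3 requires at least 6 weeks on a stable dose and says of the visit: "It may be performed before or after 8 weeks, based on when the last dose modification was performed". Dose changes are allowed up to week 4 (Protocol 7.2).

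**Who changes dose.** On the valsartan side, Protocol 4.2 says "The subjects that start from valsartan 160 mg BID will have similar scheduled visit but will stay on the same dose". Subjects from the same run-in stratum who are randomised to sacubitril/valsartan start at 100 mg BID and go to 200 mg BID where this is clinically possible (Protocol 4.1).

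**The concern.** The length of the harm window depends on dose changes, and planned dose changes are not the same in the two arms. A group with no scheduled change exists only under valsartan. If these subjects attend visit 3 early, they have less time in which an event can be recorded, yet each counts as one full subject in the denominator. The same applies to anyone who withdraws early. A visit 3 delayed for scheduling reasons has the opposite effect.

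What is at stake is how the safety tables read. With about 30 subjects per arm, a difference of one or two subjects is easily described as a difference in tolerability. The planned exposure table (SAP table list 14.3.5) would show unequal follow-up but would not correct the event tables for it. The TEAE overview by strata, also planned, would show the 160 mg stratum separately, which is where the gap in follow-up is widest and the numbers are smallest.

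**Working it through.** **The plan's own figures.** The documents give no adverse-event rate and no follow-up time by arm, so there is nothing to reproduce on this point. The one design figure, 27 per arm for the primary endpoint, does reproduce: 2 x (19.7 x (1.960 + 0.842) / 15)^2 = 27.08. It is not affected by what follows.

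**1. Earliest visit 3.** This is the week of the last dose change plus 6:
- no change: 0 + 6 = week 6
- change at visit 1 (day 14): 2 + 6 = week 8
- change at week 4: 4 + 6 = week 10

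**2. Events at an equal, constant rate.** Expected event counts are proportional to the window. The ratio is 8/6 = 1.33 for a change at visit 1 against no change, and 10/6 = 1.67 for a change at week 4 against no change.

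**3. Subjects with at least one event.** Risk over w weeks is 1 - (1 - R)^(w/8), where R is the 8-week risk. R is an assumption.

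| R (8 weeks) | 6 weeks | 10 weeks |
|---|---|---|
| 20% | 15.4% | 24.3% |
| 40% | 31.8% | 47.2% |
| 60% | 49.7% | 68.2% |

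**4. Whole-arm effect, planned dose changes only.** Let f be the share of each arm in the 160 mg stratum (an assumption; the documents give none). Suppose every sacubitril/valsartan subject and every control subject starting on 80 mg changes dose at week 2, and everyone attends at the earliest permitted time. The sacubitril/valsartan mean is then 8.0 weeks and the control mean is 6f + 8(1 - f).

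| f | Control mean (weeks) | Event-count ratio |
|---|---|---|
| 20% | 7.6 | 8/7.6 = 1.05 |
| 50% | 7.0 | 8/7.0 = 1.14 |
| 70% | 6.6 | 8/6.6 = 1.21 |

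Central case, f = 50% and R = 40%: the control risk is 0.5 x 31.8% + 0.5 x 40.0% = 35.9%, against 40.0%. In 30 subjects that is 10.8 against 12.0.

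**5. Direction.** Suppose only half of the sacubitril/valsartan arm is up-titrated and the rest are seen at week 6, while all control 80 mg starters are up-titrated and f = 20%. The means are 7.0 and 7.6 weeks, and the ratio is 7.0/7.6 = 0.92. The bias has reversed.

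**6. Serious events.** With the 30-day tail the windows are 6 x 7 + 30 = 72 days and 8 x 7 + 30 = 86 days, a ratio of 1.19. The tail dilutes the inequality but does not remove it.

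**7. Visit 3 held at week 8 for all.** The ratio is 8/8 = 1.00. Only withdrawals and delayed visits would then leave unequal follow-up.

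**The case against.** The strongest reply is that the 6-week window is a permitted extreme and not the plan. The treatment-duration text in the protocol synopsis gives subjects already on the top dose the same 2 weeks plus 6 weeks as everyone else. Protocol 4.3 puts visit 3 at about 8 weeks, Protocol 7.2 mentions only a longer treatment period, and visits are to be kept close to schedule. Only footnote 2 to Table 3 allows an earlier visit. This stands: the effect arises only if that allowance is used, and the footnote and Protocol 7.2 need to be reconciled in any case.

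A reader might infer that the tables are bound to make valsartan look safer. The documents do not support that. A sacubitril/valsartan subject who is not up-titrated is equally open to an early visit. Subjects who do not tolerate 100 mg BID are withdrawn, which shortens follow-up in that arm. A change as late as week 4 can occur in either arm.

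A reader might also infer that the SAP tests adverse events between arms, or that all collection stops at visit 3. Neither is so. The tables are descriptive, and serious events run 30 days longer.

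The effect is also small against chance. The central difference of 4.1 points compares with a standard error of sqrt(2 x 0.4 x 0.6 / 30) = 0.126, about 13 points. SAP 2.4.3 expects very few withdrawals, and the planned exposure table, visit-date listing and event listings by relative day would let a careful reader see the problem. All of this limits the weight of the point. It does not remove it, because listings expose unequal follow-up without adjusting for it.

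**Conclusion.** The point holds as a cheap improvement, not as a flaw that undermines the safety reporting. The documents allow follow-up for non-serious events to differ systematically between arms, and no planned adverse-event output takes account of it.

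Under the planned dose changes and earliest permitted visits, the spurious event-count ratio is about 1.05 to 1.21, and about one subject in 30 in the central case. This rests on assumed stratum shares of 20-70%, full up-titration, a constant event rate and, for the subject count, an assumed 8-week risk of 40%. Events clustered in the first weeks would make it smaller. It vanishes if visit 3 is held at week 8, and it reverses if many sacubitril/valsartan subjects are not up-titrated or withdraw early. Because the direction cannot be known in advance, the remedy is to report time at risk and not to assume a bias in either direction.

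**What to change.** In SAP 2.6.1, add to the TEAE overview, by arm:

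- total and median follow-up from randomisation to visit 3 or withdrawal;
- the exposure-adjusted TEAE rate, as events per 100 subject-weeks, counting only onsets within that follow-up so that numerator and denominator match;
- the same overview restricted to onsets on Days 1-42, the window open to every completer in both arms.

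State that any description of adverse-event frequency between arms is to be read alongside these outputs. Keep the crude SOC/PT and serious-event tables as planned. Rates by SOC/PT are not worth adding, because the cells will be sparse. A serious-event rate that counts the 30-day tail as time at risk should also be avoided: Protocol 8.3.4.6 stops reconciling serious events from the last subject's last visit, so time could be counted without its events.

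The cost is one or two table panels from dates already collected; no visit, treatment rule or randomisation step changes. There are three limits. The rate assumes a roughly constant hazard. The Days 1-42 overview leaves out later events, which stay in the crude tables, and does not adjust for withdrawals before Day 42. Neither output corrects for the one fewer enquiry about events when visit 2 is omitted after no up-titration.
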